14.2.12 Occurrence of Relapse

Occurrence of relapse analysis will be based on data collected on the 'Date of Visit' eCRF page.

Relapse is defined as a participant who has been discharged from the hospital with an SpO₂ of $\geq 94\%$ sustained for at least 24 hours in room air, but who must be readmitted before or on Day 60, due to either or both the following conditions:

1. Worsening oxygenation (an SpO₂ < 94% in room air), with a positive result of respiratory pathogenic nucleic acid test;

2. Worsening oxygenation (an SpO₂ < 94% in room air), with a worsening lesion on chest imaging (i.e., compared to the participant's chest X-ray or computed tomography at discharge)

Number and proportion of subjects with relapse during the study period (if first discharged) and the corresponding two-sided Wilson 95% CI will be provided by treatment group based on the ITT analysis set.

In case more than 6 events of relapse are observed, the difference in proportion of each dose to placebo will be presented with two-sided 95% CIs based on the Miettinen-Nurminen method. In addition, summary score estimates of the common difference in proportion, stratified for use of corticosteroids at a prednisone equivalent daily dosage of ≤ 15 mg or > 15 mg within 48 hours prior to randomization, AVT use in the 48h prior to randomization and country will be presented with 95% CIs based on stratified Newcombe confidence limits for the differences in proportions.

[figure not shown]
14.2.13 Occurrence of Re-hospitalization due to COVID-19 Complications

The analysis of occurrence of re-hospitalization due to COVID-19 complications will be based on data collected on the 'Hospitalization' eCRF page.

Re-hospitalization is defined as a participant who has been discharged from the hospital with an SpO₂ of $\geq 94\%$ sustained for at least 24 hours in room air, but who must be readmitted before or on Day 60, for COVID-19 related complications.

Number and proportion of subjects with re-hospitalization due to COVID-19 during the study period (if first discharged) and the corresponding two-sided Wilson 95% CI will be provided by treatment group based on the ITT analysis set.

In case more than 6 events of re-hospitalization are observed, the difference in proportion of each dose to placebo will be presented with two-sided 95% CIs based on the Miettinen-Nurminen method. In addition, summary score estimates of the common difference in proportion, stratified for use of corticosteroids at a prednisone equivalent daily dosage of ≤ 15 mg or > 15 mg within 48 hours prior to randomization, AVT use in the 48h prior to randomization and country will be presented with 95% CIs based on stratified Newcombe confidence limits for the differences in proportions.

CCI

15 Safety analysis

Safety analyses will be done on the SAF analysis set and according to the actual treatment received (see Section 8.1).

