To assess occurrence of re-hospitalizations due to COVID-19 disease complications.	Occurrence of re-hospitalization in participants during the study period (if first discharged within the 28-day study period) due to COVID-19 disease complications (Day 5 through Day 60).

AESI = adverse event of special interest; COVID-19 = coronavirus disease 2019; CRP = C-reactive protein; ECG = electrocardiogram; ECMO = extracorporeal membrane oxygenation; FiO₂ = fraction of inspired oxygen; ICU = intensive care unit; RRT = rapid response team; SAE = serious adverse event; SpO₂ = peripheral capillary oxygen saturation; TEAE = treatment-emergent adverse event.

Overall Design: This is a 2-part, Phase II double-blind, randomized, placebo-controlled study to evaluate the safety of and clinical response to M5049 tablets taken orally twice daily for 14 days in participants initially hospitalized because of moderate to severe COVID-19 pneumonia. Participants will be randomized 1:1:1 to receive M5049 50 mg, M5049 100 mg, or placebo twice daily. Part A and Part B of this exploratory study will each consist of an up to 48-hour Screening Period, a 14-day treatment period within a 28-day inpatient and/or outpatient Surveillance period, and then a 32-day inpatient and/or outpatient Safety Follow-up Period. Study participants should be provided the local standard/supportive care but cannot be on antimalarial (chloroquine-related) medications or other immunomodulating drugs (except for corticosteroids – see eligibility and coadministrations specifications). Participants on RECOVERY Trial dexamethasone dosing equivalent of corticosteroids and initiated on antiviral therapy and/or convalescent plasma for treatment of COVID-19 may be eligible for enrollment.

Sites: Site selection will be determined as information becomes available about the epidemiology of COVID-19, and sites will be activated based on the number of local/regional cases and the willingness of local Investigators to participate in the study. More specifically, epidemiology is defined by the evolving number of COVID-19 cases, the number of hospitalizations, and the number of intensive care unit admissions at each site.

Study Duration: The study will last approximately 15 months. Each participant is expected to be on study/in follow-up for 60 to 62 days.

Involvement of Special Committee(s): An internal Independent Data Monitoring Committee will be monitoring safety.

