Concomitant medication/procedure review		←-----Once daily during hospitalization. If discharged, then at study visits (e.g., Days 3, 5, 7, 10, 14, 21, 28, 44, and 60)-----→												Document what is available from the participant's chart. Record each day at approximately the same time throughout hospitalization; if participant is discharged, either via telemedicine contact or by return to study site at the times indicated only.	

Assessments and Procedures	SCR	Intervention Period (Days)							Continued Surveillance		Safety Follow-up			Relapse Admission ^a	Notes
									HD/ET	EoT					
Study Day		1	2	3	5	7	10		14	21	28	44	60	5 to 60	
Visit Window		± 6 h		± 12 h		± 24 h			+ 2 days	± 5 days	± 7 days	± 6 h			
Complete physical examination	X	X						X	X					X	Data may be collected from chart but must be verified by Clinical Investigator.
Brief physical examination			X		X	X	X			X	X				Data may be collected from the chart but must be verified by a Clinical Investigator (unless participant is discharged).
Vital signs, weight, height		←---Once daily during hospitalization (incl. predose on Day 1). --> If discharged, then at study visits (e.g., Days 3, 5, 7, 10, 14, 21, and 28)									X	X	X		Vital signs: body temperature, blood pressure, respiration rate, pulse (unless participant is discharged). Weight will be recorded at Screening, relapse admission, and Day 28 (if feasible). Height will be recorded at Screening only. Record each day at approximately the same time throughout hospitalization. All data collected from the chart. After discharge, record only at times indicated if/when participant returns to study site.
SpO ₂ saturation and FIO ₂ (or liters of O ₂)		←---Once daily during hospitalization (incl. predose on Day 1). --> If discharged, then at study visits (e.g., Days 3, 5, 7, 10, 14, 21, and 28)												X	SpO ₂ measured by pulse oximetry; record each day at approximately the same time of day throughout hospitalization and after discharge, at times indicated only if participant returns to study site (refer to Section 5).
SpO ₂ saturation in room air for 24 hours		←-----Record SpO ₂ measures after the first SpO ₂ ≥ 94% in room air during hospitalization----->												X	At any time prior to hospital discharge when SpO ₂ ≥ 94% in room air for the first time, document if participant maintains this status 24 hours later (unless participant is discharged).

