4.8 Relapse Definition

A participant who has been discharged from the hospital with an SpO₂ of $\geq 94\%$ sustained for at least 24 hours in room air, but who must be re-admitted before Day 60 due to worsening oxygenation (an SpO₂ $< 94\%$ in room air), with either a positive result of respiratory pathogenic nucleic acid test (NAT) or worsening lesions on chest imaging (compared to the participant's same modality of chest imaging [chest X-ray or computed tomography {CT}] at discharge, if available) will be counted as a respiratory relapse. For SARS-CoV-2 or any other infection, record the anatomic site from which the infection was assessed in addition to the infecting agent. The assessments in [Table 1](#) for the Relapse Visit will be performed, and assessments in [Table 1](#) will be resumed based on the participant's Day 1 of study entry.

5 Study Population

Hospitalized patients (≥ 18 to ≤ 75 years of age) with COVID-19 pneumonia not on mechanical ventilation with an SpO₂ $< 94\%$ in room air AND able to maintain a PaO₂/FiO₂ ≥ 150 (or equivalent SpO₂/FiO₂ ≥ 190) with a maximum FiO₂ 0.4. These readings may be obtained after exertion by the participant. Patients on continuous positive airway pressure should have assessments for eligibility performed while awake.

The correlation between SpO₂/FiO₂ ratio and measured PaO₂/FiO₂ ratio is high when restricted to patients with SpO₂ $\leq 96\%$, as substantial variation of PaO₂ is present in higher SpO₂ range ([Brown 2016](#)). The relationship between SpO₂/FiO₂ and PaO₂/FiO₂ was described by the following equation: $S/F = 64 + 0.84 \times (PaO_2/FiO_2)$ ([Rice 2007](#)). Maximum inhaled percentage oxygenation (FiO₂ 0.4) means patients should be on a nasal cannula or face mask without nonrebreather at ≤ 5 L/min (see guidance [Table 2](#)). (Note: face mask with nonrebreather will have a higher estimated FiO₂ [i.e., > 0.40] and therefore would be ineligible).

Table 2 Flow Rates Translated as Inhaled Oxygen Percentage (i.e., Fraction of Inspired Oxygen)

Device	Flow Rates	Delivered O ₂ ^a
Nasal cannula	1 L/min	21%-24%
	2 L/min	25%-28%
	3 L/min	29%-32%
	4 L/min	33%-36%
	5 L/min	37%-40%
	6 L/min	41%-44%
Simple oxygen face mask	6-10 L/min	35%-60%
Face mask with O ₂ reservoir (nonrebreathing mask)	6 L/min	60%
	7 L/min	70%
	8 L/min	80%
	9 L/min	90%
	10-15 L/min	95%-100%
Venturi mask	4-8 L/min	24%-40%
	10-12 L/min	40%-50%

a Percentage is approximate.

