10.4.3.10 Analysis of Inflammatory Biomarkers

Absolute values, absolute changes, and percent changes from Baseline to each time point in inflammatory biomarkers will be summarized by treatment group.

Descriptive statistics will be displayed using Box and Whisker plots.

Spaghetti plots with percent change from Baseline as well as absolute change from Baseline will also be provided by treatment group.

10.4.3.12 Analysis of Occurrence of Relapse in Participants During the Study Period (if First Discharged Within the 60-day Study Period)

Count and percentage of participants with relapse (see Section 4.8 for definition) among participants discharged before Day 28 with 95% CI will be presented by treatment group.

10.4.3.13 Analysis of Occurrence of Re-hospitalization in Participants During the Study Period (if First Discharged Within the 60-day Study Period) Due to COVID-19 Disease Complications

Count and percentage of participants who are re-hospitalized before Day 28 with 95% CI will be presented by treatment group and whether or not due to COVID-19 disease complications.

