| To evaluate clinical deterioration with M5049 compared to placebo. | 
 • Time to ICU (Day 1 through Day 28). • Time to invasive mechanical ventilation (Day 1 through Day 28). • Time to noninvasive mechanical ventilation (Day 1 through Day 28). | 
 • 14.2.5 • 14.2.7 • 14.2.6 |
| To assess the length of stay in the ICU with M5049 compared to placebo. | Total days in ICU from Day 1 through Day 60. | 14.2.8 |
| To assess the length of hospital, stay with M5049 compared to placebo. | 
 • Total days in the hospital from Day 1 through Day 60. • Time to hospital discharge from Day 1 to Day 28 | 14.2.9 |
| To evaluate modulation of biomarkers of COVID-19 inflammation with M5049 compared to placebo. | Inflammatory biomarkers (CRP, d-dimer, and ferritin) during study period (Day 1 through Day 28). | 14.2.10 |
| To evaluate modulation of select biomarkers with M5049 compared to placebo. | Biomarkers (IL-6, TNF alpha, IL-8) during study period (Day 1 through Day 28). | 14.2.11 |
| To evaluate occurrence of relapse with M5049 compared to placebo. | Occurrence of relapse in participants during the study period (if first discharged within the 60-day study period). Relapse refers to worsening oxygenation, with either a positive result of any respiratory pathogenic nucleic acid test, or worsening lesions on chest imaging with re-hospitalization. | 14.2.12 |
| To assess occurrence of re-hospitalizations due to COVID-19 disease complications. | Occurrence of re-hospitalization in participants during the study period (if first discharged within the 60-day study period) due to COVID-19 disease complications (Day 5 through Day 60). | 14.2.13 |

AESI = adverse event of special interest; COVID-19 = coronavirus disease 2019; CRP = C-reactive protein; C_{trough} = predose observed concentration; ECG = electrocardiogram; ECMO = extracorporeal membrane oxygenation; IAP = Integrated Analysis Plan; ICU = intensive care unit; IFN = interferon; CCI [REDACTED]; PK = pharmacokinetic; CCI [REDACTED] RRT = rapid response team; SAE = serious adverse event; SARS-CoV = severe acute respiratory syndrome coronavirus; SpO₂ = peripheral capillary oxygen saturation; TEAE = treatment-emergent adverse event; CCI [REDACTED]

6 Overview of Planned Analyses

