6.3 Final Analysis

This analysis will be the main analysis. All planned analyses identified in the study protocol and in this IAP will be performed only after the last participant has completed the safety follow up period with all study data in-house, and the database will be locked for the analysis.

A data review meeting will be held prior to any database lock.

7 Changes to the Planned Analyses in the Clinical Study Protocol

The inclusion of all stratification factors is identified as a potential source of problems in the implementation and interpretation of statistical models used to analyze efficacy. For this, use of corticosteroids before randomization and country will only be included, as deemed the most relevant factors, while presence of obstructive lung disease and use of antiviral therapy before randomization will be analyzed as subgroups.

8 Analysis Populations and Subgroups

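### SAP 14.2.13 adds an undeclared oxygen-saturation condition at discharge to the re-hospitalisation endpoint, so some COVID-19 readmissions cannot count

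*SAP*

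**What the plan says.** The protocol's Part B secondary endpoint (1.1 and 3.2) is "Occurrence of re-hospitalization in participants during the study period (if first discharged within the 28-day study period) due to COVID-19 disease complications", over Day 5 through Day 60. Its analysis text in 10.4.3.13 reads "Count and percentage of participants who are re-hospitalized before Day 28 with 95% CI will be presented by treatment group and whether or not" they were due to COVID-19 complications. The SAP's endpoint table (5.2) has "Occurrence of re-hospitalization in participants during the study period (if first discharged within the 60-day study period) due to COVID-19 disease complications". None of these mentions oxygen saturation at discharge.

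SAP 14.2.13 is different. It starts "Re-hospitalization is defined as a participant who has been discharged from the hospital with an" SpO2 of at least 94%, and continues "sustained for at least 24 hours in room air, but who must be readmitted before or on Day 60, for COVID-19 related complications". It names the Hospitalization eCRF page as the data source. It presents the proportion among those first discharged, based on the ITT set, with Wilson intervals by arm. Between-arm differences are added only if more than 6 events occur.

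In the protocol, the saturation condition at discharge is part of the relapse definition (4.8), where a qualifying readmission "will be counted as a respiratory relapse". SAP 14.2.12 repeats it for relapse. SAP Section 7, which lists departures from the protocol, covers only the stratification factors: "The inclusion of all stratification factors is identified as a potential source of problems in the implementation and interpretation of statistical models".

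**The concern.** A definition that appears to be carried over from a neighbouring endpoint narrows what counts as an event. The protocol asks how many discharged participants come back because of COVID-19. The SAP asks how many come back among those who left with confirmed normal room-air saturation.

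Two things are at stake. First, genuine COVID-19 readmissions are undercounted. Second, the filter is measured after randomisation. Sustained room-air SpO2 of at least 94% is itself a secondary efficacy outcome (SAP 14.2.3), so if treatment changes it, the share of readmissions eligible to count changes too. The undercount need not then be equal across arms. A lower count also makes the event trigger for the between-arm comparison harder to reach.

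**Working it through.** **Definitions side by side**

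| Source | SpO2 condition at discharge | First discharge within | Readmission counted |
|---|---|---|---|
| Protocol 1.1, 3.2 | none | 28 days | Day 5 to Day 60 |
| Protocol 10.4.3.13 | none | 60 days (heading) | before Day 28 (text), split by COVID-19 cause or not |
| SAP 5.2 | none | 60 days | Day 5 to Day 60 |
| SAP 14.2.13 | at least 94%, 24 h, room air | not limited beyond the study period | on or before Day 60 |
| Protocol 4.8, SAP 14.2.12 (relapse) | at least 94%, 24 h, room air | not limited beyond the study period | before Day 60 (Protocol); before or on Day 60 (SAP) |

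The condition in SAP 14.2.13 matches the relapse rows and none of the other re-hospitalisation rows.

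**Who is dropped**

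1. Participants discharged on oxygen or with room-air SpO2 below 94%. The documents do not say how many there will be. Users of chronic low-flow oxygen are eligible (Protocol 5.1 and 5.2), so some may exist by design.
2. Participants discharged before the 24-hour confirmation. After the first adequate room-air reading, Protocol Table 1 asks sites to "document if participant maintains this status 24 hours later (unless participant is discharged" first). For this group the missing element is a record, not necessarily a clinical state.

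Relapse has the same precondition, so it does not recover either group.

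**Size**

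The plan states no figure for this endpoint, so there is nothing to reproduce. All inputs below are assumptions:

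- f = share of discharges lacking the condition, 10-25%
- r0 = readmission rate among discharges that meet the condition, 6%
- r1 = readmission rate among those that do not, 6% or 15%
- D = 135 discharges, i.e. 90% of the planned 150

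True rate = (1 - f) x r0 + f x r1. Counted rate = (1 - f) x r0. Share lost = 1 - counted / true.

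With r1 = r0, the share lost equals f, so 10-25%. With r1 = 15%:

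- f = 10%: true 0.9 x 0.06 + 0.1 x 0.15 = 6.9%; counted 5.4%; lost 1 - 5.4/6.9 = 22%
- f = 20%: true 0.8 x 0.06 + 0.2 x 0.15 = 7.8%; counted 4.8%; lost 38%
- f = 25%: true 0.75 x 0.06 + 0.25 x 0.15 = 8.25%; counted 4.5%; lost 45%

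At f = 20%, expected events fall from 135 x 0.078 = 10.5 to 135 x 0.048 = 6.5. Under a binomial model with n = 135, the chance of more than 6 events falls from 0.91 to 0.47. With equal 6% rates it falls from 0.71 to 0.47.

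**Denominator**

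SAP 14.2.13 does not say whether discharged participants who fail the saturation condition stay in the denominator. If they do, they are automatic non-events and the proportion is biased downward.

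**The case against.** **The filter may never be programmed.** SAP 14.2.13 names only the Hospitalization page, while room-air SpO2 comes from the Pulse Oximetry and Respiratory Status pages (SAP 14.2.3). This is a fair sign of carried-over wording, but the stated definition still governs, and a programmer following it would apply the filter.

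**The readmissions are reported elsewhere.** Non-elective readmissions are SAEs (Protocol 9.1.3.2), serious TEAEs are tabulated (SAP 15.2.2), and SAP 14.2.9 counts participants with more than one admission. This stands as mitigation. None of these outputs isolates readmission for COVID-19 complications, which is the endpoint.

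**The trigger matters little.** The protocol promises only counts, percentages and intervals by arm, and the SAP gives those whatever the event count. In the example the trigger is still met about half the time, and any comparison at such counts would be imprecise. This stands; the trigger is a side effect, not the main point.

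**Differential loss is unlikely.** Allocation is randomised and site staff are blinded, so discharge practice should not differ by knowledge of arm. This is right as far as it goes. The remaining route is a treatment effect on oxygenation, which blinding does not remove. It is a possibility, not a demonstrated bias.

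**A stronger reading.** A reader might infer that the rule removes mainly the sickest discharges. The documents do not support that. The rule also drops people sent home before the 24-hour check, who may be fast recoverers, and chronic low-flow oxygen users, and no frequencies are given for any group.

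**Conclusion.** The definition in SAP 14.2.13 is wrong as written. It contradicts the protocol endpoint and the SAP's own endpoint table, and it is not declared as a change. That conclusion rests on the text alone.

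The size rests on assumed rates: 10-25% of events lost at equal readmission rates, and 22-45% at 15% against 6%, if 10-25% of discharges lack the condition. These figures illustrate what is possible and do not predict this trial. A difference in loss between arms is plausible because the filter is an efficacy variable, but it cannot be quantified from the documents.

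This is a secondary endpoint in an exploratory study, and the affected readmissions remain visible in other outputs. The correction should be made because it is nearly free, not because the trial's main conclusions depend on it.

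**What to change.** Delete the SpO2 condition from SAP 14.2.13 and keep it only in the relapse definition in 14.2.12. Count any readmission for COVID-19 complications after a first live discharge, and state that all discharged participants form the denominator.

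In the same edit, reconcile the windows. First discharge is within 28 days in Protocol 1.1 and 3.2 but within 60 days in Protocol 10.4.3.13 and SAP 5.2. Readmission is counted before Day 28 in Protocol 10.4.3.13 but through Day 60 elsewhere. State also whether the Day 5 start applies and whether the split by COVID-19 cause in Protocol 10.4.3.13 is kept.

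If the condition was intended, declare and justify it in Section 7 and add an analysis of all COVID-19 readmissions among all discharged participants.

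The cost is a few sentences in the SAP and an aligning edit to the protocol text. No new data are indicated, since 14.2.13 already draws on the Hospitalization page.

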15.1 Adverse Events

Adverse events information is collected in the 'Adverse Event' eCRF page.

Treatment-emergent adverse events (TEAE) are those events with onset or worsening dates occurring within the on-treatment period as defined in Section 9.7.

Adverse events related to study treatment are those events with relationship missing, or yes.

All analyses described in this section will be based on TEAEs if not otherwise specified. The AE listings will include all AEs (whether treatment-emergent or not).

Unless otherwise specified, TEAEs will be summarized by number and percentage of participants with the specific TEAE of interest, by treatment group, primary SOC and PT in alphabetical order.

Each participant will be counted only once within each SOC or PT. If a participant experiences more than one AE within a SOC or PT for the same summary period, only the AE with the strongest relationship or the worst severity, as appropriate, will be included in the summaries of relationship and severity.

